4.9.2 Primary Efficacy Variable – 8-week rate of RBC TI

4.9.2.1 Variable Definition

The primary variable for the assessment of efficacy is the rate of RBC TI lasting at least 8 weeks. The 8-week RBC TI rate is defined as the proportion of subjects without any RBC transfusion

during any consecutive 8 weeks (56 days) starting from Study Day 1 until subsequent anti-cancer therapy if any. The starting date of 8-week RBC TI duration must be between Study Day 1 and the date of last dose of study drug + 30 days or End of Treatment Visit whichever occurs first, or Study Day 31 if randomized but not treated.

4.9.2.2 Analysis Methods

The primary efficacy analysis is planned at 12 months after the last subject is randomized in the main study of Part 2, and the final analysis is at the End of the Study defined as 24 months after randomization of the last subject in the main study of Part 2 or anytime the sponsor terminates the study, whichever comes first.

Efficacy data in Part 1 will be descriptively summarized based on the treated population. Efficacy data the main study of in Part 2 will be compared between the imetelstat and placebo groups based on the ITT population. Any available efficacy data from Ventricular Repolarization Substudy will be descriptively summarized in addition to the efficacy data from the main study in Part 2.

Part 1 (Phase 2):

The proportion of subjects with 8-week RBC TI will be summarized with a frequency and percentage along with its 95% 2-sided exact Clopper-Pearson CI. The forest plot of the subgroup (defined in section 4.9.1.4) corresponding rate and associated 2-sided 95% CIs will be presented.

Part 2 (Phase 3):

The 8-week RBC TI rates will be summarized with frequencies and percentages along with 2-sided 95% exact Clopper-Pearson CIs for the 2 treatment groups. Difference in TI and its 95% CI will be presented using Wilson Score method [1]. The comparison will be based on a stratified CMH test adjusting for the stratification factors at a two-sided significance level of 0.05:

1. Prior RBC transfusion burden (≤ 6 or > 6 units RBC)
2. IPSS risk group (low risk or intermediate-1 risk)

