Subjects will be stratified in the randomization process according to prior RBC transfusion burden (≤ 6 or >6 units RBC) and by IPSS risk group (low versus intermediate-1) to ensure equal distribution across treatment groups. Prior RBC transfusion burden is defined as the maximum number of RBC units transfused over an 8-week period during the 16 weeks prior to C1D1 (Part 1) or Randomization (Part 2).

Blinded treatment will be used to minimize the potential influence of treatment assignment knowledge on clinical decision making, such as transfusion administration, and to reduce potential bias during data collection and evaluation of clinical endpoints; thus, ensuring the robustness and integrity of the study. The primary objective and secondary efficacy objectives of Part 2 of the main study are to compare RBC TI, time to RBC TI, and duration of RBC TI between the 2 treatment groups (imetelstat and placebo). The use of the modified IWG 2006 criteria to assess disease progression is intended to promote uniformity across study centers. It is the intent that all subjects, investigators, and study team members, except some required project roles (eg, members associated with DMC and HEC), will remain blinded to treatment group assignment at least until the primary efficacy analysis (12 months after the last subject is randomized in the main study of Part 2). As of Protocol Amendment 8, subjects, investigators, and study team members will be

unblinded after primary efficacy analysis. Upon unblinding the subjects after the primary analysis, subjects on imetelstat may continue treatment per investigator discretion. Subjects on placebo may discontinue treatment and enter the posttreatment follow-up phase of the study. The investigator will discuss treatment options with subject's discontinuing study treatment and record treatment selection as part of subsequent therapy.

Study Population

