4.12 Determination of Sample Size

Approximately 270 subjects (57 subjects already enrolled in Part 1, approximately 170 subjects in the main study of Part 2, and approximately 45 subjects in Ventricular Repolarization substudy of Part 2) will be enrolled in the study.

On the basis of historical data, RBC TI rate is expected to be approximately 7.5% [15, 16] in subjects with low or intermediate-1 risk MDS without any active treatment. The RBC TI rate with imetelstat treatment is expected to be approximately 30% based on preliminary data from [17]. The futility criteria before Amendment 2 were defined as follows: If 4 or fewer subjects among 30 subjects in Part 1 achieve RBC TI lasting at least 8 weeks, the study will be stopped unless there is compelling clinical evidence of efficacy in one or more other endpoints (eg, transfusion reduction, erythroid improvement). The initial cohort of 32 subjects enrolled into Part 1 was expanded with Amendment 2 to include an additional 25 subjects with non-del(5q) MDS and without prior exposure to either hypomethylating agents or lenalidomide who meet the revised entrance criteria, for a total of 57 subjects in Part 1.

Since data from Part 1 for this target population show clinical benefit of treatment with imetelstat, Part 2 of the study will be initiated. If the RBC TI rate of 30% with imetelstat treatment is true, the probability of passing the futility criterion is 97%. All available data will be used to support the decision.

In the main study of Part 2, approximately 170 subjects will be randomized in a 2:1 ratio to receive either imetelstat or placebo the main study of Part 2. Using a 2:1 ratio randomization and a 2-group continuity corrected Chi square test with 0.05 (2-sided) significance level, 150 subjects are needed to achieve a power of approximately 88% to detect the difference between an RBC TI rate of 30% in the imetelstat group and an RBC TI rate of 7.5% in the placebo group. After correction for a 10% drop-out rate, a total of approximately 170 subjects (115 in imetelstat group and 55 in placebo group) will be needed. The overall study power from Part 1 and the main study of Part 2 is approximately 85%.

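### With no data cut in the SAP, between-arm transfusion-independence (TI) and HI-E figures at the 24-month final analysis would mix blinded data with up to about 12 months of open-label data, mostly from the imetelstat arm

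*SAP*

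**What the plan says.** **Timing.** For Part 2, SAP 4.9.2.2 puts the primary efficacy analysis 12 months after the last main-study randomisation. It adds: "the final analysis is at the End of the Study defined as 24 months after randomization of the last subject in the main study of" that part. Protocol 11.4 gives the same two times. The next paragraph of SAP 4.9.2.2 compares Part 2 efficacy data between arms on the ITT population. It does not say which analysis time it applies to or where the data stop.

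**Window.** SAP 4.9.2.1: "The starting date of 8-week RBC TI duration must be between Study Day 1 and the date of last dose of study drug + 30 days"; the End of Treatment visit is the limit if it comes first. SAP 4.9.3.1 uses the same start limit for 24-week TI, HI-E and the 8-/16-week transfusion intervals. The window length therefore follows time on drug.

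**Unblinding.** Protocol 3.2 and 5.2, as amended by Amendment 8, unblind subjects, investigators and study team after the primary analysis. Imetelstat subjects may continue at the investigator's discretion. For the other arm: "Subjects on placebo may discontinue treatment and enter the posttreatment follow-up phase of the study". Protocol 14.2 describes only open-label imetelstat supply for main-study subjects after that. SAP 3.1 still treats unblinding as conditional, and SAP 1 names Amendment 7 as its basis.

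**Purpose of the blind.** Protocol 3.2 says blinding is there to "minimize the potential influence of treatment assignment knowledge on clinical decision making, such as transfusion administration".

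**The concern.** TI and HI-E are endpoints a subject either ever achieves or does not, so a longer window can add responders but never remove them. While both arms are treated blind, the window depends on time on drug in the same way in each, and the decision to transfuse is made without knowledge of the arm. After unblinding neither condition holds. One arm can keep opening new qualifying periods under open-label care, while the other may leave treatment and soon lose the ability to start one. The decision to transfuse is itself the endpoint, and it is then made by people who know the assignment.

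If the plan is followed as written, the final 8-week TI rate (at any time), 24-week TI rate and HI-E rate by arm would not be blinded, equal-opportunity comparisons. The exposure matters most for 24-week TI and HI-E. These are the two gatekeepers for PFS and OS in SAP 4.9.1.3, which does not say at which analysis time they are tested.

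**Working it through.** **1. The plan's own figures (SAP 4.12).** Inputs: "Using a 2:1 ratio randomization and a 2-group continuity corrected Chi square test with 0.05 (2-sided) significance level"; "an RBC TI rate of 30% in the imetelstat group and an RBC TI rate of 7.5% in the placebo group"; "150 subjects are needed to achieve a power of approximately 88"%.

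- Pooled rate: (0.075 + 2 × 0.30)/3 = 0.225. Difference: 0.225.
- Uncorrected placebo-arm n for 88% power: [1.960 × √(0.225 × 0.775 × 1.5) + 1.175 × √(0.075 × 0.925 + 0.30 × 0.70/2)]² / 0.225² ≈ 44.0.
- Continuity-corrected: (44.0/4) × [1 + √(1 + 3/(44.0 × 0.225))]² ≈ 50.5, so 51, and 3 × 51 = 153 in total. For 87% power the total is 150.
- Power at 50/100: 87.6% by formula, 88.7% by exact enumeration. The stated 88% reproduces.
- Drop-out: 150/0.90 = 167, rounded to about 170. Overall power: 0.88 × 0.970 = 85.3%, where 0.970 is the chance of at least 5 responders among 30 at a 30% rate.

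None of these depends on the 24-month analysis.

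**2. Calendar.** 24 − 12 = 12 months between the two analyses. This is a ceiling on the open-label period, because unblinding follows the primary analysis. The last subject randomised has 12 blinded months by then, and all others have more.

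**3. The arms after unblinding.**

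| | Imetelstat | Placebo |
|---|---|---|
| Treatment | may continue, open-label | may stop |
| New qualifying period may start | while on drug, plus up to 30 days | up to 30 days after last dose |
| Period already running | continues | continues until a transfusion or subsequent anti-cancer therapy |
| Transfusion data once off treatment | to first posttreatment transfusion | to first posttreatment transfusion |

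The last two rules apply to both arms. The imbalance arises because only one arm has a reason to stay on treatment.

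**4. Which endpoints are exposed.**

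- 8-week TI in the first 24 and 48 weeks (SAP 4.9.3.2): not exposed, since both windows end before 12 months.
- 8-week TI at any time: exposed, probably modestly. The latest Part 1 onset was week 33.1 (Protocol 1.1.5), although follow-up there was limited.
- 24-week TI: more exposed. A period starting at week 33.1 ends at 33.1 + 24 = week 57.1, after week 52. An 8-week responder who stays on drug can also become a 24-week responder later.
- HI-E: exposed, with no fixed-window version.
- Amount, relative change and best interval: summarised or plotted only (SAP 4.9.3.2), so no formal comparison is affected.

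**5. Can the size be derived?** It needs the share of imetelstat non-responders still on drug at unblinding (q) and their chance of a new 8-week TI afterwards (r). Neither document gives these. As an illustration only, assume no drug effect and a TI rate of p₀ in both arms at the blinded cut. The imetelstat rate then becomes p₀ + (1 − p₀) × q × r. The last column is the chance that a hypothetical unstratified Mantel-Haenszel test (115 vs 55, two-sided 0.05, exact enumeration) rejects in favour of imetelstat.

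| p₀ | q | r | Imetelstat rate | Extra responders of 115 | Rejects for imetelstat |
|---|---|---|---|---|---|
| 7.5% | equal windows | – | 7.5% | 0 | 2.0% |
| 7.5% | 20% | 3% | 8.0% | 0.6 | 2.7% |
| 7.5% | 35% | 7.5% | 9.9% | 2.8 | 5.9% |
| 7.5% | 50% | 15% | 14.4% | 8.0 | 23% |

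With p₀ = 3% the same corners give 1.1% to 38% (0.4% with equal windows). With p₀ = 15% they give 2.6% to 15% (2.2% with equal windows). For orientation on q, exponential time on drug with the Part 1 median of 8 cycles (8 × 28/30.4375 = 7.36 months) leaves 32% on drug at 12 months, 18% at 18 and 10% at 24. The results run from negligible to large, so the direction is clear and the size is not.

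**The case against.** The case against has several parts.

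- **No second TI test is scheduled.** SAP 4.9.1.3 tests the primary hypothesis once at 0.05, and the blind holds to that point. This stands. A reader might infer that the primary result is compromised or that a repeat TI test is planned at 24 months; neither document says so. What remains is a general sentence comparing efficacy between arms with no cut, and gatekeepers with no stated analysis time.
- **Placebo windows do not close at unblinding by rule.** This stands. Stopping is permitted rather than required, the start window lasts up to 30 days after the last dose, and a running period continues. In practice closure is likely to follow soon, because no further placebo supply is described for main-study subjects.
- **A fixed-window analysis already exists.** This stands for 8-week TI in the first 24 and 48 weeks. It does not cover 24-week TI or HI-E.
- **Late new responders should be few.** This is plausible for 8-week TI: Part 1 onset was early, and those kept on drug are probably enriched for existing responders, who cannot count twice. It is weaker for 24-week TI.
- **It is partly a version lag.** SAP 2.0 is dated 15 September 2022 and Amendment 8 is dated 13 December 2022. That explains the gap but does not close it.

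A reader might also gauge the size from how chance TI grows over the first year of observation. That period lies wholly within blinded follow-up, so it says nothing about the months after unblinding.

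**Conclusion.** The concern holds in limited form. Following the SAP as written, final between-arm figures for 8-week TI at any time, 24-week TI and HI-E would combine a blinded comparison with up to about 12 months of open-label observation, nearly all of it on imetelstat. The bias would mainly favour imetelstat. This assumes that some imetelstat subjects continue, that most placebo subjects stop once unblinded, and that the general comparison sentence in SAP 4.9.2.2 applies at the final analysis.

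The blinded 12-month primary test, the design power and the fixed 24-/48-week 8-week TI analysis are not affected. No magnitude should be attached, because the inputs it needs are not in the documents. The point is worth fixing before the final analysis, but it is not a threat to the primary result.

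**What to change.** Update the SAP to Amendment 8 and add a short paragraph to 4.9.2.2 and 4.9.3.2 stating that:

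1. the TI and HI-E hypothesis tests, including the 24-week TI and HI-E gatekeepers, are done once, at the primary analysis;
2. any between-arm TI or HI-E comparison shown at the final analysis uses data up to the common primary-analysis clinical cutoff, before general unblinding;
3. later transfusion data, including amount, relative change and best interval, are shown descriptively and labelled open-label.

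A common cutoff is better than each subject's own unblinding date. Protocol 5.2 allows emergency unblinding of individual subjects who then stay in the study, and a per-subject date would cut their data early.

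The cost is one SAP paragraph and one date cut in programming. The downside is that some 24-week TI periods that finish after the cutoff, including some that began blinded, are reported only descriptively.

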4.9.2.3 Sensitivity Analysis

Sensitivity analyses will be performed for Part 2 to evaluate the robustness of the primary analysis and includes:

- CMH test of 8-week based on MITT analysis set in the case there are subjects who were dosed, but did not receive any assigned treatment;
- CMH test of 8-week based on PP analysis set;
- CMH estimate of the odds ratio of 8-week RBC TI with the stratification factors and the associated 95% CI;
- Comparison of 8-week RBC TI based on CMH test adjusted by values of prior RBC transfusion burden and IPSS risk group recorded on the eCRF.

- Comparison of 8-week RBC TI based on CMH test without adjusting for the baseline stratification factors.

4.9.3 Key Secondary Efficacy Variables

4.9.3.1 Variables Definition

24-week RBC TI rate

24-week RBC TI rate is defined as the proportion of subjects without any RBC transfusion during any consecutive 24 weeks (168 days) starting from Study Day 1 until subsequent anti-cancer therapy if any. The starting date of 24-week RBC TI must be between Study Day 1 and the date of last dose of study drug + 30 days or End of Treatment Visit whichever occurs first, or Study Day 31 if randomized but not treated.

Time to 8-week (24-week) RBC TI

Time to 8-week (24-week) RBC TI is defined as the interval from Study Day 1 to the first day of the first 8-week (24-week) RBC TI period.

Duration of RBC TI

Duration of RBC TI is defined as the first day of the longest RBC TI period to the date of the first RBC transfusion after the TI period starts. Subjects who have not had an RBC transfusion ending the TI period at the time of analysis or who withdraw from the study will be censored at the date of the last transfusion evaluation or the day before the first date of subsequent anticancer therapy if given, whichever occurs first.

Rate of hematologic improvement, including HI-E, per modified IWG 2006

The modified IWG 2006 criteria [5] for HI define specific responses of cytopenia in the three hematopoietic lineages: erythroid (HI-E), platelet (HI-P), and neutrophil (HI-N). Rate of hematologic improvement is defined as the proportion of subjects who achieve HI-E, or HI-P, or HI-N.

HI-E is defined as a hemoglobin (Hb) increase of at least 1.5 g/dL above pretreatment and lasts at least 8 weeks or reduction of at least 4 units of RBC transfusion units/8 weeks compared with the prior RBC transfusion burden. A valid 8-week period must start before the date of last dose of study drug + 30 days or End of Treatment Visit whichever occurs first, or Study Day 31 if randomized but not treated, and ends before the first transfusion in posttreatment follow-up or the first day of subsequent anti-cancer therapy whichever occurs first. Pretreatment Hb level is defined as the average of all the Hb values (from transfusion history, local, and central lab) in the 8 weeks prior to first dose date, including the value on first dose date (Part 1 or Part 2) and excluding values that were within 14 days after transfusion (thus considered to be influenced by transfusion) for all

treated subjects. If there were no Hb values that met this definition of not being influenced by transfusions, then the baseline value (the last non-missing Hb, or the average if multiple values from the same date, from local or central lab collected on or before the first dose) is used. For subjects who have been randomized but not treated with any study drug, the last non-missing Hb, or the average if multiple values from the same date, from local or central lab collected on or before the randomization date will be used for pretreatment Hb.

HI-P is defined as absolute increase in platelet count of $\geq 30 \times 10^9/L$ for subjects starting with $> 20 \times 10^9/L$ platelets or increase from $< 20 \times 10^9/L$ to $> 20 \times 10^9/L$ and by at least 100% lasts at least 8 weeks.

HI-N is defined as at least 100% increase in neutrophil count and an absolute increase $> 0.5 \times 10^9/L$ lasts at least 8 weeks.

Progression or relapse after HI is defined as at least 1 of the following, in the absence of another explanation, per modified IWG 2006: a) at least 50% decrement from maximum response levels in granulocytes or platelets; b) reduction in Hb by ≥ 1.5 g/dL; c) transfusion dependence.

Rate of HI-E per revised IWG 2018

For LTB subjects (who received 3 to 7 RBC units in the 16 weeks prior to study entry):

- Clinically meaningful HI-E response per revised IWG 2018 [4] is defined as 16-week RBC TI, i.e. subjects without any RBC transfusion during any consecutive 16 weeks.

For HTB subjects (who received ≥ 8 RBC units in the 16 weeks prior to study entry):

- Major HI-E response per revised IWG 2018 is defined as 16-week RBC TI.
- Minor HI-E response per revised IWG 2018 is defined as a reduction by at least 50% of RBC units over a 16-week period compared with the 16 weeks prior to Study Entry.

Rate of Complete remission (CR), Partial remission (PR) or Marrow complete remission (mCR)

It is defined as the proportion of subjects who achieve CR, PR or mCR per modified IWG 2006. The analysis will be performed in the ITT analysis set as well as in subjects with bone marrow blasts $> 5\%$ at baseline.

Progression Free Survival (PFS)

Progression free survival, defined as the time interval from Study Day 1 to the first date of disease progression or death from any cause, whichever occurs first. Subjects who received subsequent anti-cancer therapy prior to documented progression will be censored at the date of last evaluable response assessment or disease progression status conducted on or prior to the initiation of subsequent anti-cancer therapy. If subjects do not have any adequate post-baseline assessment and did not die, PFS will be censored at Study Day 1.

PFS will be computed as date of PFS event or censoring – Study Day 1+ 1.

Overall Survival (OS)

OS is defined as the interval from Study Day 1 to death from any cause. Survival time of living subjects will be censored on the last date a subject is known to be alive or lost to follow-up.

Time to progression to AML

Time to progression to AML is defined as the interval from Study Day 1 to the date of AML progression. Subjects who received subsequent anti-cancer therapy prior to documented progression will be censored at the date of last evaluable response assessment or disease progression status conducted on or prior to the initiation of subsequent anti-cancer therapy. If subjects do not have any adequate post-baseline assessment, time to progression to AML will be censored at Study Day 1.

Amount and relative change in RBC transfusions

Amount of RBC transfusions per 8-week (16-week) is defined as the total number of RBC transfusion units in a given 8-week (16-week) interval during study.

Relative change in RBC transfusions per 8-week = (amount of RBC transfusions per 8-week – prior RBC transfusion burden) / prior RBC transfusion burden multiply by 100%.

Relative change in RBC transfusions per 16-week = (amount of RBC transfusions per 16-week – total RBC transfusion units in 16 weeks prior to study entry) / total RBC transfusion burden in 16 weeks prior to study entry multiply by 100%.

The starting date of an 8-week (16-week) interval must be between Study Day 1 and date of last dose of study drug + 30 days or End of Treatment Visit whichever occurs first, or Study Day 31 if randomized but not treated, and the ending date must be before the first transfusion in posttreatment follow-up or the first day of subsequent anti-cancer therapy whichever occurs first. Note that prior RBC transfusion burden is defined as the maximum number of RBC units transfused over an 8-week period during the 16 weeks prior to Cycle 1 Day 1 (C1D1) for subjects enrolled in Part 1 or the day of randomization for subjects enrolled in Part 2.

Rate of myeloid growth factor usage

Rate of myeloid growth factor usage is defined as the proportion of subjects who received any myeloid growth factors starting from Study Day 1. Duration of myeloid growth factor administered starting from Study Day 1 will also be summarized.

PRO measure of interest

See details in Section 4.11.6.

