9.3.1.1. Transfusions

Transfusion data will be collected during the treatment and posttreatment periods throughout the study as specified in the Time and Event Schedules. Transfusion is monitored at each visit for imetelstat infusion (every 4-week cycle), at each disease evaluation visit, and at all unscheduled visits during treatment. During the posttreatment phase, transfusion data will be collected every 4 to 6 weeks until the first transfusion in follow-up. Enhanced operational monitoring will be implemented to seek transfusion information from other documented sources. Enhanced and continuous medical review will be implemented to identify any sudden but unsustained increase of Hb values and to query whether transfusion has occurred.

Data to be collected include the date of transfusion, number of units and type of blood products transfused and the pre-transfusion Hb and platelet count. Red blood cell transfusions may be administered based on Hb level, investigator's assessment of the subject's clinical signs and symptoms, and local clinical practice. As the volume of 1 unit of RBC transfusion may vary regionally, one unit is defined as the amount that is intended to raise Hb by approximately 1 g/dL

in an adult patient (ie, one standard pRBC unit or equivalent). The total number of RBC units required over rolling 8-week time periods will be calculated to identify subjects who achieve RBC TI or transfusion reduction.

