9.3.1.2. Hemoglobin Assessment

Hemoglobin levels will be measured as detailed in the Time and Event Schedules for Part 1 and Part 2 as per Table 1 and Table 3, respectively. For a given subject, the same local laboratory should be used for each hematology assessment throughout the study, to the extent possible. In Part 2, in addition to the local laboratory, a central laboratory will be used for all planned Hb assessments. Subjects enrolled in the Ventricular Repolarization substudy (after Protocol Amendment 7) are not required to send samples for central Hb laboratory assessments. Treatment decision and investigator-assessed disease response evaluations will be based on the local laboratory results (see Section 11.13 for adjudication of assessments by independent review). Sponsor assessed HI-E will primarily be based on the central laboratory results. Investigator- and sponsor assessments based on local laboratory data will also be presented.

Hematologic improvement-erythroid (HI-E) response is defined as i) a Hb rise of at least 1.5 g/dL above the pretreatment level and lasts at least 8 weeks or ii), reduction of at least 4 units of RBC transfusion units/8 weeks compared with the prior RBC transfusion burden (criterion adapted from the modified IWG 2006 [Attachment 5]). Pretreatment Hb level is defined as the average of all the Hb values in the 8 weeks prior to C1D1, including the value on C1D1 (Part 1 or Part 2) and excluding values that were within 14 days after transfusion (thus considered to be influenced by transfusion). If there were no Hb values that met this definition of not being influenced by transfusions, then the baseline value is used.

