4.9.1.3 Multiple Comparisons/Multiplicity

Testing of Primary Endpoint for Part 2 (Phase 3)

For Part 2, the primary hypothesis is that imetelstat will increase the rate of RBC TI as compared to placebo in transfusion dependent subjects with low or intermediate-1 risk MDS that is relapsed/refractory to ESA treatment. The primary efficacy hypothesis on 8-week RBC TI will be tested at 0.05 (two-sided) for Part 2.

Testing of Secondary Endpoints for Part 2 (Phase 3)

For Part 2, a sequential gate-keeping procedure and Hochberg procedure will be implemented to ensure that the overall type I error rate for the secondary endpoints is controlled. Let α be the critical type I error rate 0.05 (2-sided). 24-week RBC TI and rate of HI-E per modified IWG 2006 are the most important secondary endpoints, thus will be used as gate keepers and be tested at the α level sequentially. 24-week RBC TI will be the first gate keeper and rate of HI-E per modified IWG 2006 will be the second gate keeper. If the nominal p-value is $< \alpha$ for 24-week TI, then rate of HI-E will be tested next at the α level. If the nominal p-value is $< \alpha$ for rate of HI-E as well, the remaining selected secondary hypotheses (PFS, and OS) will be tested using a Hochberg procedure [2].

In summary, the secondary endpoints as the gate keepers which will be tested sequentially at 0.05 (2-sided) are:

1. 24-week RBC TI
2. Rate of HI-E per modified IWG 2006

If the above two gate keepers are significant, the following endpoints will be tested using a Hochberg procedure:

- PFS
- OS

In general, Hochberg procedure is conducted as the following steps:

1. Suppose we have H_1, \dots, H_m null hypotheses tested and P_1, \dots, P_m as their corresponding p-values. We order these p-values in increasing order and denote them by $P_{(1)}, \dots, P_{(m)}$.
2. For a given significance level α , find the largest k such that $P_{(k)} \leq \alpha / (m+1-k)$.
3. Reject the null hypothesis for all $H_{(i)}$ for $i=1, \dots, k$.

Note that Hochberg procedure does not require the order of hypotheses and it controls the overall type I error when conducting multiple comparisons at the given significance level α if the p-values are independent or positively correlated.

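### The hemoglobin limb of HI-E, the second gatekeeper, removes post-transfusion values from the pretreatment Hb but not from on-study Hb, so a transfused subject with unchanged need can count as a responder

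*SAP*

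**What the plan says.** SAP 4.9.1.3 sets the order of testing: "24-week RBC TI will be the first gate keeper and rate of HI-E per modified IWG 2006 will be the second gate keeper". PFS and OS are tested, by Hochberg, only if both gatekeepers succeed. The gatekeeper is the whole HI-E rate. A subject meets it through the hemoglobin limb or through a fall of at least 4 RBC units per 8 weeks from the prior burden.

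SAP 4.9.3.1 gives the hemoglobin limb: "HI-E is defined as a hemoglobin (Hb) increase of at least 1.5 g/dL above pretreatment and lasts at least 8 weeks". Protocol 9.3.1.2 agrees: "a Hb rise of at least 1.5 g/dL above the pretreatment level and lasts at least 8 weeks". In both documents the pretreatment Hb is an average over the preceding 8 weeks, "excluding values that were within 14 days after transfusion". The SAP draws this average from transfusion-history, local and central values. There is a fallback: "If there were no Hb values that met this definition of not being influenced by transfusions, then the baseline value" is used, which may itself be influenced by a transfusion.

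Nothing comparable governs on-study Hb. Under SAP 4.9.3.1 the valid 8-week window must end before the first transfusion in posttreatment follow-up or before subsequent anti-cancer therapy. A transfusion during treatment does not end it. SAP 4.9.3.2 does apply the 14-day exclusion on study, but only to a descriptive variable, the Hb rise in TI responders. Protocol 9.3.1.2 bases sponsor-assessed HI-E primarily on the central laboratory. The SAP does not name the on-study Hb source for HI-E.

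**The concern.** Values soon after a transfusion are left out of the pretreatment Hb because they reflect the transfusion and not the marrow. The same reasoning holds on study. Leaving them in there compares a largely uninfluenced starting level with follow-up that may be influenced.

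The threshold is within reach of ordinary transfusion practice. Protocol 9.3.1.1 states that "one unit is defined as the amount that is intended to raise Hb by approximately 1 g/dL", so a 2-unit episode moves Hb by about 2 g/dL against a threshold of 1.5. Every subject enters needing at least 4 units per 8 weeks.

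Two things are at stake. One is the meaning of the responder count. The other is power at a gate that decides whether PFS and OS can be formally tested. The sensitivity analyses listed in SAP 4.9.2.3 and 4.9.3.2 cover 8-week and 24-week TI; none addresses HI-E.

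**Working it through.** **The plan's own figure.** The documents state no power or sample size for HI-E. The stated power for 8-week TI (about 88%, 150 subjects, 2:1, 30% v 7.5%, continuity-corrected chi-square) reproduces:
- Pooled rate 0.225; null SE = √(0.225 × 0.775 × (1/50 + 1/100)) = 0.0723.
- Alternative SE = √(0.075 × 0.925/50 + 0.30 × 0.70/100) = 0.0591; continuity correction 0.015.
- z = (0.225 − 0.015 − 1.96 × 0.0723)/0.0591 ≈ 1.155, so power is 87.6%.

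That figure does not depend on the HI-E definition.

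**Can a subject with unchanged need qualify?**
- From the documents: 1 g/dL per unit; at least 4 units per 8 weeks at entry; from Cycle 3, hematology scheduled only on Day 1 of each 4-week cycle (Protocol Table 3).
- Assumed: 2 units every 28 days, linear decline back to trough.
- Rise above trough d days after transfusion = 2 × (1 − d/28).
- d = 1, 3, 5, 7 gives +1.93, +1.79, +1.64, +1.50 g/dL.

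A Day 1 sample up to 7 days after a transfusion therefore meets the threshold. Three Day 1 samples 28 days apart span 56 days. The subject still receives 4 units per 8 weeks, so the transfusion limb is not met and the hemoglobin limb alone creates the response.

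**How often?** This was simulated for subjects with no true change: episodes every 14, 21 or 28 days on average, irregular meaning an interval SD of 3 to 5 days, Hb noise SD 0.35 g/dL, and protocol visits over about a year. A subject is net new only if the transfusion limb has not already classed the subject as a responder.

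| Setting | False HI-E |
|---|---|
| 2 units, irregular intervals, scheduled Hb only | about 2-8% net |
| 2 units, rigid intervals, scheduled Hb only | 0-22% net |
| 3 units, irregular intervals, scheduled Hb only | about 7-27% net |
| 14-day exclusion also applied on study | about 0-3% gross |
| Documented pre-transfusion Hb counted on study | 0% |

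The 0% under rigid intervals is the 14-day case. There every value lies within 14 days of a transfusion, so the fallback supplies an influenced baseline as well.

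**Effect at the gate.** Let p be the true HI-E rate and f the false-positive rate among true non-responders. The observed rate is p + (1 − p)f. With the same f in both arms, the difference becomes (p₁ − p₀)(1 − f), which is zero when p₁ = p₀. The figures below use 115 v 55 subjects, two-sided 0.05, and the unstratified normal approximation without continuity correction. The 71% is the Part 1 rate in the target population (Protocol 1.1.5); the placebo rates are assumed.

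| f imetelstat / placebo | 71% v 50%: observed | Power | 71% v 40%: observed | Power |
|---|---|---|---|---|
| 0 / 0 | 71.0 v 50.0 | 75.9% | 71.0 v 40.0 | 97.5% |
| 5% / 5% | 72.5 v 52.5 | 72.5% | 72.5 v 43.0 | 96.2% |
| 10% / 10% | 73.9 v 55.0 | 68.9% | 73.9 v 46.0 | 94.5% |
| 5% / 10% | 72.5 v 55.0 | 61.5% | 72.5 v 46.0 | 91.8% |

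Example, last row, 71% v 50%: 0.71 + 0.29 × 0.05 = 0.7245 and 0.50 + 0.50 × 0.10 = 0.55, a difference of 0.1745 in place of 0.21.

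**The case against.** The strongest reply is that the trial already records the values that would defeat a false response. Protocol Table 3 requires pre-transfusion Hb to be documented, and the SAP already uses transfusion-history Hb for the pretreatment average. A subject transfused every few weeks has troughs on record inside any 8-week window, and a rise that falls back to trough has not lasted 8 weeks. With those values counted, false responses vanish in the simulation. This stands as a reason to settle the data source. It does not close the gap, because the SAP never says those values enter on-study HI-E and the protocol points primarily to the central laboratory.

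Other safeguards are partial. Samples are to be drawn before transfusion only where feasible. Medical review of sudden Hb rises looks for unreported transfusions and does not remove values after recorded ones. Transfusion dependence defines relapse after HI and does not prevent HI from being assigned. The revised IWG 2018 HI-E uses no Hb values, but it is not the gatekeeper.

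It is also fair that the definition tracks its source: the IWG footnote in Protocol Attachment 5 attaches the not-influenced condition to pretreatment counts only. This is a gap in the trial's operational rule, not a departure from IWG.

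A reader might infer that the rule inflates type I error, or that false responders will fall mainly in the placebo arm. The documents support neither. With no treatment effect, transfusion patterns and misclassification should be alike in the two blinded arms. An excess on placebo is plausible if imetelstat works, but the documents give no placebo HI-E rate and no on-study Hb pattern.

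**Conclusion.** The asymmetry is in the current text of both documents and reaches a confirmatory endpoint. As written, HI-E can include transfused subjects whose need has not changed. The consequence is dilution of the treatment difference and a responder count that is hard to interpret.

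The size cannot be fixed from the documents. It depends on units per episode, the timing of transfusions relative to visits, and whether pre-transfusion Hb is used on study. With scheduled values only and irregular 2-unit transfusions, a few percent of such subjects would be net new false responders; with 3 units the figure could reach about a quarter. The threat to the gate is modest if the true HI-E difference is wide and material if it is nearer 20 percentage points.

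Gross hemoglobin-limb rates, which run much higher, should not be read as the effect on the gatekeeper. HI-E has a second limb, and subjects who already meet it are not newly misclassified. The point deserves correction in the SAP; it does not undermine the primary analysis.

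**What to change.** In SAP 4.9.3.1, add to the HI-E definition:

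> On-study Hb values within 14 days after an RBC transfusion are excluded from HI-E (Hb). Documented pre-transfusion Hb values are included, as they are for pretreatment Hb. An 8-week Hb response requires at least 2 evaluable values spanning the period, all at least 1.5 g/dL above pretreatment.

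State that the 14-day rule applies to pre-transfusion values too, as it does for pretreatment Hb, and name the on-study laboratory source or sources. The minimum of two values is a proposal; the documents set none. Report the hemoglobin and transfusion-reduction limbs separately beside the combined rate, in line with the recommendation in Protocol Attachment 5 to report individual response patterns.

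The cost is a short SAP addition, minor programming, and somewhat fewer hemoglobin-limb responders in both arms. No new data are needed, since transfusion dates and pre-transfusion Hb are already collected. The change should be fixed before unblinding.
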